4.4. Subject Number and Identification

Subjects will have a unique identification number used at Screening. Subjects will be assigned a subject number prior to the first dosing occasion. Assignment of subject numbers will be in ascending order and no numbers will be omitted (e.g., Subjects 0101, 0102, 0103). Replacement subjects will be assigned a subject number corresponding to the number of the subject he/she is replacing plus 1000 (e.g., Subject 1101 replaces Subject 0101).

Subjects will be identified by subject number only on all study documentation. A list identifying the subjects by subject number will be kept in the Site Master File.

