Medical or scientific judgment is to be exercised in deciding whether serious adverse event reporting is appropriate in other situations such as important medical events that may not be immediately life-threatening or result in death or

hospitalization but may jeopardize the subject or may require medical or surgical intervention to prevent 1 of the other outcomes listed in the above definition. These events are typically to be considered serious.

Examples of such events include invasive or malignant cancers, intensive treatment in an emergency room or at home for allergic bronchospasm, blood dyscrasias, or convulsions that do not result in hospitalization, or development of drug dependency or drug abuse.

Recording Adverse Events and Serious Adverse Events

Adverse Event and Serious Adverse Event Recording

- When an adverse event or serious adverse event occurs, it is the responsibility of the Investigator to review all documentation (e.g., hospital progress notes, laboratory, and diagnostics reports) related to the event.
- The Investigator will then record all relevant adverse event/serious adverse event information in the Event electronic Case Report Form (eCRF).
- The Investigator must assign the following adverse event attributes:
 - Adverse event diagnosis or syndrome(s), if known (if not known, signs or symptoms)
 - Dates of onset and resolution (if resolved)
 - Did the event start prior to first dose of investigational product, other protocol-required therapies
 - Assessment of seriousness
 - Severity (or toxicity defined below)
 - Assessment of relatedness to the investigational product(s) and/or study-mandated procedures
 - Action taken
 - Outcome of event.
- If the severity of an adverse event changes from the date of onset to the date of resolution, record as a single event with the worst severity on the appropriate eCRF.
- It is not acceptable for the Investigator to send photocopies of the subject's medical records to Sponsor in lieu of completion of the appropriate eCRF page.
- If specifically requested, the Investigator may need to provide additional follow-up information, such as discharge summaries, medical records, or extracts from the medical records. In this case, all subject identifiers, with the exception of the subject number, will be blinded on the copies of the medical records before submission to the Sponsor.

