^g A full physical examination at Check-in and a symptom-directed physical examination on Day 6 and at EOS/ET.

^h Dose administration of rosuvastatin is to occur during the mornings of Days 1 and 6 following an overnight fast of at least 10 hours. On Day 6, rosuvastatin administration will occur immediately after administration of sotorasib.

ⁱ Dose administration of sotorasib is to occur during the morning of Day 6 following an overnight fast of at least 10 hours.

^j Blood samples for determination of rosuvastatin plasma concentrations and PK parameters will be collected: Predose (Hour 0), 0.5, 1, 2, 3, 4, 5, 6, 8, 10, 12, 24, 36, 48, 72, 96, and 120 hours postdose following administration of rosuvastatin on Days 1 and 6.

^k Blood samples for determination of sotorasib plasma concentrations and PK parameters will be collected: Predose (Hour 0), 0.5, 1, 2, 3, 4, 5, 6, 8, 10, 12, 24, 36, and 48 hours postdose following administration of sotorasib on Day 6. The PK sample collected 30 minutes postdose will have a sampling window of \pm 2 minutes, samples collected from 1 through 3 hours postdose will have a sampling window of \pm 5 minutes, samples collected from 4 through 10 hours postdose will have a sampling window of \pm 10 minutes, and samples collected from 12 through 48 hours postdose will have a sampling window of \pm 20 minutes. Times of all PK samples will be recorded to the nearest minute.

^l Adverse events will be recorded from initiation of study treatment on Day 1 until EOS completion. Serious adverse events will be recorded from the time the subject signs the informed consent form through 30 days after the last dose of study treatment or the EOS (whichever is later).

^m Prior and concomitant medication administration will be recorded beginning at informed consent. In addition, all Investigator-approved medications taken by a subject within 30 days or 5 half-lives (whichever is longer) prior to enrollment administration for over-the-counter or prescription medications, and 30 days prior to enrollment for herbal medicines (e.g., St. John's wort), vitamins, and supplements, will be recorded on the subject's electronic Case Report Form.

ⁿ Performed prior to dosing.

^o Assessment to be performed at the EOS visit or if a subject is withdrawn early from the study.

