8.6. Safety and Tolerability Assessments

8.6.1. Adverse Events

All AEs will be coded using the Medical Dictionary for Regulatory Activities (MedDRA) Version 24.0 (or higher if a new version is issued during the study; see the DMP for more details). All AEs will be assigned a severity grade using Common Terminology Criteria for Adverse Events (CTCAE) Version 5.0 (or higher if a new version is issued during the study; see the protocol for more details).

A treatment-emergent adverse event (TEAE) will be defined as an AE that starts during or after dosing, or starts prior to dosing and increases in severity after dosing.

A treatment-related TEAE will be defined as a TEAE with a relationship related to the study treatment, as determined by the investigator.

All AEs will be listed. In addition to the data recorded in the database, the listings will include derived onset time and duration. Onset time will be calculated from the time of dosing for TEAEs only.

CONFIDENTIAL

The frequency of subjects with TEAEs and the number of TEAEs will be summarized for the following categories:

- TEAEs (overall, serious, leading to discontinuation, and leading to death) by treatment
- TEAEs by severity and treatment
- Treatment-related TEAEs (overall, serious, leading to discontinuation, and leading to death) by treatment
- Treatment-related TEAEs by severity and treatment

The frequency of subjects will be summarized separately for TEAEs and treatment-related TEAEs by the following:

- System organ class, preferred term, and treatment
- Preferred term and treatment

For the AE data the following rules will apply:

- For the derivation of treatment-emergent status (applicable to all AEs): If the start date/time of an AE is incomplete or missing, an AE will be assumed to not be a TEAE, unless the incomplete start date/time or the end date/time indicates an AE started after dosing.
- For the derivation of treatment-related status (applicable to TEAEs only): If the study treatment relationship for a TEAE is missing, a TEAE will be assumed to not be a treatment-related TEAE.

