- For the derivation of onset time (applicable to TEAEs only): If the start date/time of a TEAE is missing, onset time will not be calculated. If the start date/time of a TEAE is incomplete, where possible, the minimum possible onset time will be calculated and presented in '≥DD:HH:MM' format (eg, if the date/time of dosing is 01MAY2019/08:00 and recorded start date/time of a TEAE is 03MAY2019, then the minimum possible onset time will be calculated by assuming a TEAE started at the first hour and minute of 03MAY2019 [03MAY2019/00:00], thus will be presented as onset time ≥01:16:00 in the listing). If the start date of a TEAE is the same as the date of dosing but the start time of a TEAE is missing, an onset time will be presented as '≥00:00:01'. Any clock changes will be accounted for in the derivation.
- For the derivation of duration (applicable to all AEs): If the end date/time of an AE is missing, duration will not be calculated. If the start or end date/time of an AE is incomplete, where possible, the maximum possible duration will be calculated and presented in '≤DD:HH:MM' format (eg, if the start of an AE date/time is 01MAY2019/08:00 and its recorded end date/time is 03MAY2019, then the maximum possible duration will be calculated by assuming an AE ended at the last hour and minute of 03MAY2019 [03MAY2019/23:59], thus will be presented as

Page 18 of 23

duration ≤02:15:59 in the listing). Any clock changes will be accounted for in the derivation.

- For the calculation of TEAE summary statistics: If the severity of a TEAE is missing, that TEAE will be counted under the 'missing' category.
- For the calculation of TEAE summary statistics: If a subject experienced multiple TEAEs with the same preferred term for the same treatment, this will be counted as 1 TEAE for that treatment under the maximum severity recorded.

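### SAP 8.6.1 promises a number of TEAEs but counts subject-by-term combinations, and its default for an unclear onset leans towards fewer TEAEs

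*SAP*

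**What the plan says.** SAP 8.6.1 announces two quantities side by side: "The frequency of subjects with TEAEs and the number of TEAEs will be summarized for the following categories". The categories are TEAEs overall, serious, leading to discontinuation and leading to death, and TEAEs by severity, each by treatment, with the same again for treatment-related TEAEs. The system organ class and preferred term tables are different: "The frequency of subjects will be summarized separately for TEAEs and treatment-related TEAEs by the following".

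At the end of the same section, a rule that applies to TEAE summary statistics in general says: "If a subject experienced multiple TEAEs with the same preferred term for the same treatment, this will be counted as 1 TEAE". The single count goes under the highest severity recorded.

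On onset, an AE whose start is incomplete or missing is "assumed to not be a TEAE, unless the incomplete start date/time or the end date/time indicates an AE started after dosing". A later rule in the section, on displaying onset time, says that a TEAE dated on a dosing date but without a clock time is shown as ≥00:00:01.

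The protocol is not consistent on when AE recording begins. Section 7.2.1 has non-serious AEs recorded from enrollment. Section 3.1 places enrollment at subject number allocation, and Section 4.4 adds: "Subjects will be assigned a subject number prior to the first dosing occasion". Footnote l of Appendix 8 has AEs recorded from the first study treatment on Day 1, and then says: "Serious adverse events will be recorded from the time the subject signs the informed consent form". Appendix 1 lists an item for the investigator to complete on each event: "Did the event start prior to first dose of investigational product, other protocol-required therapies".

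**The concern.** A reader of the study report will take a number of TEAEs as a number of events. Under the counting rule it is not one. Because the term-level tables give subjects only, no summary described in the SAP text gives the event count at all. The loss is also uneven across grades: when a term repeats at different grades, only the highest survives, so the severity table understates the milder events.

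The onset default matters less, because it needs missing data to act. When it does act, it takes an event out of the TEAE tables and leaves it in the listing only, so it always works in the favourable direction. The usual choice where onset is unclear is the opposite one.

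Safety and tolerability of rosuvastatin alone and of the combination is a secondary objective, and these tables are the descriptive evidence for it.

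**Working it through.** **The plan's own figures.** The only numbers in this part of the SAP are two worked examples. From 01MAY2019 08:00 to 03MAY2019 00:00 is 40 h, which is 1 day 16 h, or 01:16:00. From 01MAY2019 08:00 to 03MAY2019 23:59 is 63 h 59 min, or 02:15:59. Both reproduce.

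**Counting rule, complete data.** Reported count = events − repeats of the same term within subject and treatment.

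1. One subject, one treatment, headaches of grades 1, 1 and 2: 3 − 2 = 1. Grade 1 falls from 2 to 0, grade 2 stays at 1, and 2/3 = 67% of this subject's events are not counted.
2. An invented set of eight records. Subject 1 has three headaches (grades 1, 1, 2) on rosuvastatin and one nausea (grade 1) on the combination. Subject 2 has four diarrhoea records (grades 1, 1, 2, 1) on the combination.

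| | Every record | SAP rule |
|---|---|---|
| Total | 8 | 3 |
| Rosuvastatin | 3 | 1 |
| Combination | 5 | 2 |
| Grade 1 | 6 | 1 |
| Grade 2 | 2 | 2 |
| Subjects with any TEAE, rosuvastatin | 1 | 1 |
| Subjects with any TEAE, combination | 2 | 2 |

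The number of subjects with any TEAE does not move. Only the event column changes its meaning.

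3. The documents give no repeat rate. Assuming 10 events with 0, 2 or 4 repeats, the reported number is 10 − 0 = 10, 10 − 2 = 8 or 10 − 4 = 6.

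**Onset default.** Three cases follow from the text.

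1. Start missing, end on Day 3. An end date bounds the start only from above, so it cannot show that the AE began after dosing. The default applies.
2. Start and end both missing. The default applies.
3. Start dated Day 1, no time. The date alone does not show onset after dosing, so the default read by itself gives non-TEAE. The ≥00:00:01 display convention, however, presupposes that such an AE is a TEAE. The two rules do not fit together. Appendix 8 says only that doses are given in the morning; assuming a dose between 07:00 and 10:00, the share of the day after the dose is (24 − 7)/24 = 71% down to (24 − 10)/24 = 58%.

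The default also sits badly with footnote l of Appendix 8. If recording starts with treatment on Day 1, a non-serious AE in the database is already post-dose. If recording starts at enrollment, as Section 7.2.1 says, pre-dose AEs can be present and some rule is needed; serious AEs are recorded from consent in either case.

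No rate of missing dates is given. One reclassified subject is 1/14 = 7.1 percentage points, or 1/12 = 8.3 with 12 subjects, and only if that subject has no other event in the category.

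**The case against.** The counting rule is stated openly, so the SAP can be said to define its own unit. Protocol 8.4 asks only for the number and percentage of subjects, and allows subject-level data in place of tables when incidence is low. Every AE is listed, and the TFL shells, a separate document not included here, may carry a footnote. All of this limits the damage, but none of it makes the label right: the SAP itself promises a number of TEAEs beside the subject frequency and then computes something else.

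On onset, the objection is that missing dates should be rare with confinement, daily questioning and required attributes. That stands, and it is why this is the smaller point.

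Several stronger readings are tempting and not supported:

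- *An undated-time AE on Day 1 certainly drops out of the tables.* The ≥00:00:01 convention points the other way. The text is inconsistent, not settled.
- *The required item on onset before first dose resolves everything.* Its wording in Appendix 1 covers investigational product and other required therapies, but the sample SAE form refers to the first dose of IP alone. Sotorasib is first given on Day 6, so under that reading an AE from Days 1 to 5 would be marked as pre-dose.
- *The causality default is an error.* SAP 8.6.1 says: "If the study treatment relationship for a TEAE is missing, a TEAE will be assumed to not be a treatment-related TEAE". SAP 8.1.2 allows exceptions to its missing-category rule where they are specifically stated, and relatedness is a required attribute.
- *AEs cannot be assigned to a treatment.* Dosing is not tied to Day 1 or Day 6, and an AE starting on Day 3 and worsening on Day 7 could be placed in either column. But the tables are plainly meant to be by treatment, and the shells or the eCRF may settle the rule. This is a request for clarification only.

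**Conclusion.** The counting point holds as written and needs no assumption about data quality: the column described as the number of TEAEs is a count of subject-by-preferred-term combinations within treatment, at maximum severity. Its size depends on how often terms repeat, which the documents do not say; with no repeats there is no difference.

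The onset default holds as a secondary point. It runs in the favourable direction, is inconsistent with the onset-time convention, and rests on a recording start that the protocol states in two ways.

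The severity is minor. A reader might infer that events are hidden or that the safety conclusion is at risk. The documents do not support that: all AEs are listed, the number of subjects with any TEAE is unaffected by the counting rule, missing fields should be rare, and SAP 8.6.6 plans no inferential safety analysis.

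**What to change.** In SAP 8.6.1, before database lock:

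- Limit the collapse rule to subject counts and maximum severity, and count every TEAE record in the event column. Alternatively, keep the rule and relabel the column as subject-by-preferred-term combinations.
- Treat an AE with an unclear onset as a TEAE unless the available dates show that it began before the Day 1 dose and did not worsen afterwards. Use the item on onset before first dose only if the eCRF defines it against the first dose of either product on Day 1. Align the ≥00:00:01 convention with this rule.
- Reconcile protocol Section 7.2.1 with footnote l of Appendix 8 on when AE recording starts.
- If a rule for treatment columns is added, assign each TEAE to the most recent dose before onset or worsening, and state where undated AEs go. Appendix 1 keeps one record at worst severity and lists no worsening date, so an AE ongoing at the Day 6 dose may need a flag.

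The cost is a few sentences in the SAP and matching table programming, plus one reconciliation in the protocol text. Reported counts will be slightly higher, and one subject with many repeats can dominate an event count, so subject frequency should stay beside it.

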8.6.2. Clinical Laboratory Parameters

All clinical laboratory parameters, will be listed, as applicable; any value outside the clinical reference range will be flagged. Separate listings will be provided for any parameter for which there is any individual subject value outside the respective clinical reference range

Summary tables by timepoint will be provided for clinical chemistry and hematology parameters.

Values recorded as $\langle x, \leq x, \rangle x$, or $\geq x$ will be displayed in the listings as recorded. For the derivation of listing flags, all calculations, and presentation in the figures, $\langle x \rangle x$ and $\leq x \rangle x$ will be set to 0, whereas $\geq x \rangle x$ and $\geq x \rangle x$ values will be set to x.

8.6.3. Vital Signs Parameters

All vital signs parameters will be listed, as applicable; any value outside the clinical reference range will be flagged.

Summary tables and boxplots by treatment and timepoint will be provided by treatment group for all vital signs parameters as applicable.

8.6.4. 12-lead Electrocardiogram Parameters

All 12-lead ECG parameters will be listed; any value outside the clinical reference range will be flagged.

Summary tables by timepoint will be provided for all 12-lead ECG parameters.

8.6.5. Other Assessments

Medical history will not be listed.

All other safety and tolerability assessments not detailed in the above sections will be listed only.

8.6.6. Safety and Tolerability Statistical Methodology

No inferential statistical analyses are planned.

SAP CONFIDENTIAL Covance Study: 8461525 Protocol Reference: 20200426

9. INTERIM ANALYSES

No interim analyses are planned.

10. SIGNIFICANT CHANGES FROM THE PROTOCOL-SPECIFIED ANALYSES

There were no significant changes from the protocol-specified analyses.

16.1.9.2. Quality Tolerance Limit Definitions

Parameter	Justification for Parameter	Unit Tolerance
Minimum number of evaluable subjects needed.	A shortfall in the overall number of subjects could have had a significant impact on interpretation of the primary endpoint because of limited/insufficient exposure.	N: 12

CONFIDENTIAL

Protocol Reference: 20200426

Final Page 23 of 23
